9.4 Exclusion Criteria

Subjects will be excluded from the study if *any* of the following criteria are met:

1. Known hypersensitivity or contraindication to aspirin, heparin and bivalirudin, thienopyridines, cobalt, nickel, platinum, iridium, chromium, molybdenum, polymer coatings (e.g. BioLinx™), anticoagulations or a sensitivity to contrast media, which cannot be adequately pre-medicated
2. History of an allergic reaction or significant sensitivity to drugs such as zotarolimus, rapamycin, tacrolimus, everolimus, or any other analogue or derivative
3. Subjects who are judged to have a lesion that prevents complete inflation of an angioplasty balloon or proper placement of the stent or stent delivery system
4. Unprotected left main coronary artery disease (no patent bypass graft(s) to one or more branches of the left coronary artery; the left anterior descending or circumflex artery, with an obstruction greater than 50% in the left main coronary artery)
5. Subjects with planned PCI of three vessel disease (includes staged procedures*)
6. Currently participating in an investigational drug or another device study that has not completed the primary endpoint or that clinically interferes with the current study endpoints

Note: Studies requiring extended follow-up for products that were investigational, but have since become commercially available, are not considered investigational studies.

7. Planned surgery that would cause interruption in recommended DAPT duration per current guidelines

* Note: Subjects with planned PCI of three vessel disease are excluded from participating in the RESOLUTE ONYX Post Approval Study (PAS). This exclusion extends to staged procedures (even if started prior to study enrollment). Therefore, any subjects with a previous PCI may not participate if the intention is to treat two addition coronary vessels at a later date as part of RESOLUTE ONYX PAS. There are no exclusions for previous PCI or limits to timepoints on when a previous PCI was performed relevant to enrollment in RESOLUTE ONYX PAS as long all enrollment criteria are observed.

In addition to the general exclusion criteria listed above, subjects will be excluded from the Bifurcation Cohort if *any* of the following criteria are met:

1. Planned two stent technique (main branch and side branch) of a bifurcation
2. Subjects with more than one bifurcation lesion
3. Trifurcation lesions
4. Planned treatment of any additional lesion(s) in the bifurcation target vessel(s), inclusive of branches within 12 months
5. Target lesion(s) are located in native vessel(s) within 5 mm distal to anastomosis with a bypass graft (including but not limited to saphenous vein graft or a left/right internal mammary artery (LIMA/RIMA)) and/or with more than 40% diameter stenosis anywhere within the graft
6. Impaired renal function (serum creatinine > 2.5 mg/dl or $221 \mu\text{mol/l}$) or on dialysis

7. Left ventricular ejection fraction (LVEF) $\leq 30\%$

10 Study Procedures

10.1 Schedule of Events

Subjects will be assessed by telephone, e-mail, and/or office visit at the intervals listed in Table 1.

Table 1: Schedule of Treatments and Assessments

Follow-up Interval	Window
30 days	± 5 days
6 months	± 14 days
12 months	± 30 days
24 months	± 30 days
36 months	± 30 days

10.2 Data Collection

The clinical procedures that must be performed and laboratory tests that must be drawn for all subjects prior to the stenting procedure are listed below and in Table 2.

RESOLUTE ONYX Post-Approval Study (ONYX PAS)

Clinical Investigation Plan

Version 6.0

Page 33 of 87

Medtronic

Table 2: Schedule of Treatments and Assessments

	Baseline	Procedure ¹	Discharge	Follow-up ²
Eligibility criteria	●			
Informed Consent	●			
Medical & cardiac history	●			
Angina Status	●			●
Pregnancy Test ³	●			
Angiogram	●	●		
SAE data ⁴	●	●	●	●
Device deficiency data	●	●	●	●
Cardiac biomarkers ⁵	● ⁶		● ⁷	
12 lead ECG ⁸	●		●	
Anti-platelet medication	●	●	●	●
Serum Creatinine	●			
LV Ejection Fraction ⁹	●			

1. End of procedure is defined as removal of the guide catheter
2. Follow-up subject contact is planned at 30 days, 6, 12, 24 and 36 months. Subject contact includes phone call, email or clinic visit (for radial access subjects, assess radial artery patency at the 30 day follow-up if completed as office visit)
3. For women of childbearing potential only
4. SAE collection will start when the subject has signed the Informed Consent or Data Release Form
5. CK values should be collected if standard hospital practice. In addition to CK values, CK-MB and/or Troponin values must be collected.
6. Cardiac biomarkers will be collected pre-procedure within 72 hours.
7. Post-procedure cardiac biomarkers will be collected at two times. The first collection must occur 3 or more hours post-procedure; the second collection must occur 4 hours after the first but prior to 24 hours post-procedure or at discharge whichever comes first.
8. A 12 lead ECG will be performed within 24 hours post-procedure.
9. LV Ejection fraction value (not a range) within 6-months prior to the index procedure

Relevant source documents including baseline ECG (screening and discharge), event ECG (most abnormal ECG and last ECG recorded), angiogram films and medical records (including admission, discharge notes, reports and biomarker values) will be requested for reported or suspected events including revascularizations, deaths or any (suspected) myocardial infarction or (suspected) stent thrombosis that occurs after the index procedure for adjudication purposes by a Clinical Events Committee (CEC).

10.3 Scheduled Follow-up Visit Windows

Data analyses include follow-up visits, regardless of whether the visit occurs within the window. Therefore, a late visit is preferred over a missed visit but must be accompanied by a deviation report. Follow up visit windows are listed in Table 1 and are based on days post-implant.

10.4 Subject Screening

All subjects evaluated for potential PCI of the coronary arteries should be screened for study eligibility. A qualified member of the investigational site's research team will review the subject's medical history and screen for study eligibility. A screening failure case report form (CRF) will be provided to the site to maintain a record of each subject screened by the site along with the reason(s) for study exclusion.

10.5 Prior and Concomitant Medications/Therapies

Antiplatelet medication should be administered according to hospital routine and in line with the applicable guidelines on percutaneous coronary interventions and the Instructions for Use of the device.

The following antiplatelet therapy is recommended:

- A. A minimum of 75 mg of Aspirin daily (within 24 hours prior to the procedure) and continued indefinitely post procedure
- B. A market approved antiplatelet loading dose within 24 hours prior to the procedure or immediately post procedure (within 30 minutes of last catheter removal). Antiplatelet should be prescribed as indicated by the current society guidelines and applicable Instruction for Use or longer as per physician's decision
- C. During the index procedure, heparin or bivalirudin will be administered as per hospital standard of care. A GP IIb/IIIa receptor blocker may be administered at the Investigator's discretion

All other co-medication usage is at the Investigators discretion and should be done according to hospital routine.

10.6 Subject Consent

All subjects must complete the consent process prior to undergoing any study-related procedures. Sites must comply with local regulatory requirements (ISO14155: 2020 in Europe and 21 CFR 50 in the United States) and local IRB/EC policies for obtaining informed consent.

In advance of the consent discussion, the subject should receive the IRB/EC approved Subject Informed Consent Form. During the consent discussion, the investigator or his/her designee (only in geographies where allowed) must fully inform the subject of all pertinent aspects of the study. If a subject is illiterate, an impartial witness must be present during the entire informed consent discussion. All items discussed in the Subject Informed Consent Form must be explained. The language used shall be as non-technical as possible and must be understandable to the subject and the impartial witness, where applicable. Subject Informed Consent Forms should be made available in subject's native language.

Neither the investigator nor the investigation site staff shall coerce or unduly influence a subject to participate or to continue to participate in the clinical study. The informed consent process shall not appear to waive the subject's rights.

When the subject decides to participate in the clinical study, the site's current IRB/EC and Medtronic-approved Subject Informed Consent Form must be signed and personally dated by the subject (or their legally authorized representative) and investigator/or designee. If applicable, the witness shall also sign

and personally date the consent form to attest that the information in the Subject Informed Consent Form was accurately explained and clearly understood by the subject, and that informed consent was freely given.

After all persons have signed and dated the Subject Informed Consent Form, the investigator/or designee must provide the subject with a copy of the signed and dated Subject Informed Consent Form. The consent process should be documented in the subject's medical record.

Medtronic will inform the investigators whenever information becomes available that may be relevant to the subject's continued participation in the study. The investigator or designee should inform the subject in a timely manner.

Medtronic will revise the written Subject Informed Consent Form whenever new information becomes available that may be relevant to the subject's continued participation in the study. The revised information will be sent to the investigator for approval by the IRB/EC. After approval by the IRB/EC, a copy of this information must be provided to the participating subjects, and the informed consent process as described above needs to be repeated.

Refer to Appendix 2: Subject Informed Consent for the IC template.

10.7 Enrollment

Refer to Section 9.2 Subject Enrollment. A log of all subjects enrolled in the study should be maintained. Enrollment can be a stand-alone visit or can occur on the same day as the baseline visit. Once consent is obtained, report adverse events/deaths, study deviations and subject exits as they occur.

10.8 Baseline

Refer to section 10.2 Data Collection for the information collected at the baseline visit.

Treatment of the target lesion(s) will be in accordance with standard hospital policy for the care of interventional cardiology subjects unless otherwise specified in this Investigational Plan. Procedure start time is defined at the point of guide catheter insertion.

The angiography and stenting procedure should be performed according to the IFU for the Resolute Onyx™ stent and if applicable, the Angiographic Core Lab procedures in Appendix 6.

If the procedure involves treating a bifurcation lesion, a single-stent strategy⁴ (the Provisional Stenting Technique provided under Appendix 7) will be followed.

Both ACC/AHA⁵ and ESC⁵ revascularization guidelines currently recommend provisional stenting as the preferred procedure strategy for patients who are candidates for a bifurcation intervention.

Bifurcation lesions in subjects enrolled in the Bifurcation Cohort should be treated with provisional stenting.

This provisional technique recommends stent placement in the Main Branch (MB), finalized with proximal optimization technique (POT), followed by placement of a second stent if inadequate results are found in the side branch (SB) such as:

- threatened closure of the side branch
- cases of Thrombolysis in Myocardial Infarction (TIMI) flow <3
- dissection type B or worse, or
- residual stenosis more than 80%, or
- abnormal assessment by fractional flow reserve (FFR) ≤ 0.80 or instant wave-free ratio (iFR) ≤ 0.89

RESOLUTE ONYX Post-Approval Study (ONYX PAS)

Clinical Investigation Plan

Version 6.0

Page 36 of 87

Medtronic

All standard ancillary devices (e.g., guidewires, sheaths/guiding catheters, pre-dilatation balloons, etc.) used during the preparation and procedure should be used in accordance with the manufacturer's instructions.

When bailout is needed, and a second stent is required for the side branch, the recommended technique is culotte, however the anatomy characteristics and/or operator preference may dictate a different technique (e.g DK Crush or other)

Careful stent sizing is important to successful stenting. In general, the stent size should be chosen to match the diameter of the reference vessel and to correspond with the length of the lesion. The appropriate Resolute Onyx™ stent size selected for the target lesion must be \geq 3 mm longer than the lesion length in order to provide 1.5 mm of stent coverage on either side of the lesion.

Available Resolute Onyx™ stent sizes are listed in Table 3.

Table 3: Resolute Onyx™ Stent Size Matrix

Nominal Expanded Inner Diameter (mm)	Stent Length (mm)								
	8	12	15	18	22	26	30	34	38
2.0	✓	✓	✓	✓	✓	✓	✓		
2.25	✓	✓	✓	✓	✓	✓	✓	✓	✓
2.5	✓	✓	✓	✓	✓	✓	✓	✓	✓
2.75	✓	✓	✓	✓	✓	✓	✓	✓	✓
3.0	✓	✓	✓	✓	✓	✓	✓	✓	✓
3.5	✓	✓	✓	✓	✓	✓	✓	✓	✓
4.0	✓	✓	✓	✓	✓	✓	✓	✓	✓
4.5		✓	✓	✓	✓	✓	✓		
5.0		✓	✓	✓	✓	✓	✓		

Post-dilatation may be performed at the Investigator's discretion with an appropriately sized (length and diameter) non-compliant balloon to assure that the stent is in full contact with the vessel wall. Do not use the Resolute Onyx stent delivery system for post-dilatation.

The end of the procedure is defined as the time the guide catheter is removed from the subject.

10.8.1 Additional procedure criteria for bifurcation lesions

- Only one bifurcated lesion is allowed. An additional (non-bifurcated) lesion in a different epicardial vessel may be treated for a maximum of two treated vessels during index procedure. For subjects with planned treatment of two lesions, the first lesion (non-bifurcated) must be treated successfully and the subject must be clinically stable before treatment of the second lesion (bifurcated) is attempted.
- Any additional lesion(s) in the bifurcation target vessel(s), inclusive of branches, can only be treated after 12 months post-procedure.
- Any repeat revascularization should be clinically- driven, (e.g. positive stress test and or functional significance of the stenosis as evaluated by FFR)

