Term	Definition
	such as hemorrhage, embolism, thrombosis, or rupturing aneurysm, that persists more than 24 hours.
Target lesion	Any lesion treated or attempted to be treated during the study procedure with the Resolute Onyx™ Stent. The target lesion is the treated segment starting 5 mm proximal to the stent and ending 5 mm distal to the stent.
Target lesion failure (TLF)	Cardiac death, target vessel myocardial infarction (Q wave and non-Q wave), or clinically driven target lesion revascularization (TLR) by percutaneous or surgical methods.
Target lesion revascularization (TLR)	Repeat PCI or CABG to the target lesion. See also clinically driven target lesion revascularization.
Target vessel	
The arterial segment and any branches and/or parent vessel that possess the target lesion.
 
Note: Side branches less than 2.0 mm in diameter will not be considered 'significant' and therefore the disease in these vessels will not be considered significant.
 
Note: Grafts to the parent vessel will be treated as side branches to that vessel for Inclusion/Exclusion Criteria evaluation, and for event evaluation and reporting – such as TV related MI and TV Revasc assessments.

Target vessel failure (TVF)	
The composite endpoint comprised of cardiac death, target vessel myocardial infarction, or clinically-driven target vessel revascularization by percutaneous or surgical methods. Target vessel failure will be reported when ANY of the following events occur:
 
 • Recurrent MI occurs in territory not clearly attributed to a vessel other than the target vessel. • Cardiac death not clearly due to a non-target vessel endpoint. • Target vessel revascularization is determined.
Thrombus (intracoronary)	
Non-occlusive thrombus: Intracoronary thrombus is defined as a (spheric, ovoid or irregular) non-calcified filling defect or lucency surrounded by contrast material (on three sides or within a coronary stenosis) seen in multiple projections, or persistence of contrast material within the lumen, or a visible embolization of intraluminal material downstream.
 
Occlusive thrombus: TIMI 0 or TIMI 1 intra-stent or proximal to a stent up to the most adjacent proximal side branch or main branch (if originating from the side branch).

Total occlusion	A lesion with no flow (TIMI 0). Total occlusions are usually classified as persisting less than or more than 3 months (chronic total occlusion).

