5.1.2 Primary Endpoint(s)

The primary endpoint for all subjects in the Primary and XLV Cohorts participating in this study is Target Lesion Failure (TLF), defined as cardiac death, target vessel myocardial infarction (Q wave and non-Q wave), or clinically driven target lesion revascularization (TLR) by percutaneous or surgical methods, at 12 months.

The primary endpoint for subjects participating in the Bifurcation Cohort is Target Vessel Failure (TVF) at 12 months.

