10.13 Deviation Handling

A study deviation is defined as an event where the Investigator or site personnel did not conduct the study according to the Clinical Investigational Plan, applicable laws or regulations, or the Investigator Agreement.

Regulations require that Investigators maintain accurate, complete and current records, including documentation of any deviations from the investigational plan including the date of and reason for the deviation. The deviations must be reported to the sponsor on the CRF.

Investigators are required whenever possible to obtain prior approval from the Medtronic Clinical Research Department before initiating changes in or deviations from the investigational plan, except

where necessary to protect the life or physical well-being of a subject in an emergency. Such approval will be documented in writing and maintained in the study files. Prior approval is not expected in situations where unforeseen circumstances are beyond the Investigator's control (e.g., subject did not attend scheduled follow-up visit, blood sample lost by laboratory, etc.), however, the event, is still considered a deviation.

Deviations shall be reported to Medtronic regardless of whether medically justifiable, pre-approved by Medtronic, or taken to protect the subject in an emergency. Deviations to protect the life or physical well-being of the subject in an emergency must be reported to Medtronic and the IRB/EC within five working days.

Subject-specific deviations will be reported on the non-compliance CRF. Deviations that are not subject-specific (e.g. unauthorized use of an investigational device outside the study, unauthorized use of an investigational device by a physician who has not signed an Investigator Agreement, etc.) will be reported to Medtronic in writing. Investigators will also adhere to procedures for reporting study deviations to their IRB/EC in accordance with their IRB/EC requirements.

The investigational site's compliance with the clinical investigational plan will be assessed on an ongoing basis. Corrective and preventive action plans will be developed and implemented to secure compliance. In case of serious noncompliance, the sponsor may decide to stop subject enrollment at an investigational site based on its assessment.

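### Protocol 10.8.1 drops the word 'planned' from the 12-month rule on additional lesions; followed literally, it could push clinically driven revascularizations past the TVF window

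*Protocol*

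**What the plan says.** Protocol 10.8.1, second bullet: "Any additional lesion(s) in the bifurcation target vessel(s), inclusive of branches, can only be treated after 12 months post-procedure". The sentence carries no limit to planned treatment, names no cohort and gives no exception for clinical need.

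The eligibility rule on the same subject, Protocol 9.4, Bifurcation Cohort exclusion 4, reads: "Planned treatment of any additional lesion(s) in the bifurcation target vessel(s), inclusive of branches within 12 months". It stands in a list whose opening words are "subjects will be excluded from the Bifurcation Cohort if". SAP 5.1.2 repeats this exclusion, with its limit to planned treatment.

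The third bullet of 10.8.1 says: "Any repeat revascularization should be clinically- driven, (e.g. positive stress test and or functional significance of the stenosis as evaluated by FFR". It sets an indication but no timing, and it does not say how it relates to the second bullet.

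On the endpoint, Protocol 5.1.2 says: "The primary endpoint for subjects participating in the Bifurcation Cohort is Target Vessel Failure (TVF) at 12 months". The Glossary defines TVF as "cardiac death, target vessel myocardial infarction, or clinically-driven target vessel revascularization by percutaneous or surgical methods". Its entries for target vessel and for clinically driven target vessel revascularization (TVR) cover the whole vessel and its branches.

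**The concern.** An eligibility rule about what is intended at baseline reappears in 10.8.1 as a rule about what may be done during follow-up. Suppose a subject has an untreated lesion elsewhere in the target vessel, with no treatment planned at baseline. At month 8 the lesion causes ischemia, but it is not an emergency. Under 9.4 nothing stands in the way of treating it. Under the literal second bullet of 10.8.1 it waits until month 12 has passed.

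Two things are at stake. One is care: 11.3 says that participants receive the same treatment as patients outside the study, and a literal hold would conflict with that. The other is the primary endpoint. Treatment at month 8 that met the Glossary criteria would be a TVF event, whereas the same treatment after month 12 would fall outside the 12-month count. The shift can go in one direction only, toward fewer events. The cohort is a single arm tested against a fixed goal, so no control arm shares the shift.

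**Working it through.** **1. The two rules side by side**

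| Feature | 9.4 exclusion 4 and SAP 5.1.2 | 10.8.1, second bullet |
|---|---|---|
| Limited to planned treatment | Yes | No |
| Limited to the Bifurcation Cohort | Yes | No; the heading covers bifurcation lesions in general |
| Exception for clinical need | Not needed, since only plans are barred | None |

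**2. How far the literal bar reaches**

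- *Target lesion:* the Glossary says "The target lesion is the treated segment starting 5 mm proximal to the stent and ending 5 mm distal to the stent". Repeat treatment inside that segment is not treatment of an additional lesion, so it is not barred.
- *Other TVF components:* cardiac death and target vessel myocardial infarction count as before.
- *Emergencies:* 10.13 waives prior sponsor approval "where necessary to protect the life or physical well-being of a subject in an emergency".
- *Non-emergencies:* 10.13 also lets a deviation go ahead with sponsor approval. The treatment would then take place within 12 months and count as TVF.

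What remains is a non-target lesion in the target vessel, not planned for treatment at baseline, later clinically indicated but not an emergency, and held past 12 months without an approved deviation.

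**3. The plan's own figure**

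Inputs from Protocol 14.2.3 and 14.5: one-sided alpha 0.05, true rate 16.3%, goal 24.5%, 180 evaluable of 200, exact binomial upper bound. For x events in n subjects, the one-sided 95% exact upper bound is the 0.95 quantile of Beta(x + 1, n − x). The cohort passes if this is below 24.5%.

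| n | Largest passing count | Upper bound | Next count | Upper bound |
|---|---|---|---|---|
| 180 | 34 | 24.34% | 35 | 24.94% |
| 200 | 38 | 24.15% | 39 | 24.69% |

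Power at n = 180 is P(X ≤ 34 | 0.163) = 85.1%, which matches the stated 85%. 180 / (1 − 0.10) = 200 also matches. No stated figure is wrong on this point.

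**4. Illustration: one deferred event**

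The documents give no number of deferred revascularizations, so one is an assumption. Take a true rate of exactly 24.5%, where the cohort should fail. If one actual event is removed from the count, the cohort passes when the full count is at most one above the limit.

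- n = 180: P(X ≤ 34) = 4.52%. Adding P(X = 35) = 2.02% gives P(X ≤ 35) = 6.54%, so 4.5% becomes 6.5%.
- n = 200: P(X ≤ 38) = 3.94%. Adding P(X = 39) = 1.71% gives P(X ≤ 39) = 5.65%, so 3.9% becomes 5.7%.

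One deferral changes the result only when the full count is exactly 35 of 180, or 39 of 200.

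**The case against.** The strongest reply is that this is a drafting slip that no site would act on. Section 10.8.1 is a set of procedure criteria under the Baseline section, and its first bullet speaks of lesions planned for treatment. The third bullet foresees later revascularization on elective grounds, with no time limit. TVR and TVF are assessed at discharge, 30 days and 6 months as well as at 12 months, and revascularizations reported during follow-up are adjudicated. Section 11.3 promises ordinary care. All of this presupposes that target vessel revascularization can happen before 12 months. That stands as evidence of intent, and it is why the point is minor.

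It does not settle the text. The third bullet concerns repeat revascularization, which need not include the first treatment of a different lesion, and neither bullet says which governs.

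A second reply is that 10.13 offers a route even on the literal reading, through emergency or sponsor-approved deviations. That also stands, so deferral is not the only possible outcome. But clinically indicated treatment should not have to be handled as a protocol deviation.

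A reader might infer that the protocol withholds indicated care, or that the TVF result is biased by a material amount. The documents support neither. They do not show that any treatment was or would be deferred, and they give no rate from which to size an effect. A reader might also give the missing cohort limit equal weight. It has little endpoint effect: the Primary and XLV Cohorts use Target Lesion Failure, whose revascularization component is confined to the target lesion, and subjects pooled from them must already meet the Bifurcation Cohort criteria.

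**Conclusion.** The bullet is wrong as written, and the point is minor. Section 10.8.1 is broader than the rule in 9.4 and SAP 5.1.2, and nothing in the protocol says which applies when an additional lesion becomes clinically indicated within 12 months. The effect on TVF depends on a site following the bullet literally and not using a deviation under 10.13. Any such effect would favour meeting the 24.5% goal. Its size cannot be derived and may be zero. The change of about two percentage points in the chance of passing rests on an assumed single deferral and a true rate exactly at the goal. The stated power and sample size are unaffected.

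**What to change.** Replace the second bullet of 10.8.1 with:

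*For subjects in the Bifurcation Cohort, treatment of an additional lesion in the bifurcation target vessel(s) or their branches may not be planned within 12 months post-procedure. Clinically driven revascularization is not to be deferred and counts toward TVF.*

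This restores the two limits in 9.4 and settles how the second and third bullets fit together. The cost is one bullet, taken through the routine amendment steps in Protocol 16.6 or issued as a clarification to sites. Eligibility, data collection and the SAP do not change.
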